To address not only whether the intervention works, but also how the intervention works, we will also test the exploratory mediation models depicted in Figure 1 and Figure 2.

RQ9 Is the effect of MBT-PP (compared to TAU) on externalising and internalising behaviours in children aged 8-14 (as measured by the SDQ 'difficulties' scale) mediated by parent mentalising, parent anger expression, parent report IPC, child perception of IPC, parenting style, or parent emotional adaptation?

RQ10 Is the effect of MBT-PP (compared to TAU) on wellbeing in children aged 8-14 (as measured by the Stirling Children's Well-being Scale) mediated by parent mentalising, parent anger expression, parent report IPC, child perception of IPC, parenting style, or parent emotional adaptation?

Figure 1. Examining the mechanisms by which MBT-PP may improve children’s externalising and internalising behaviours

[figure not shown]
[figure not shown]

Figure 2. Examining the mechanisms by which MBT-PP may improve children’s psychological well-being

Design

Table 2. Trial design

Trial design, including number of arms		Pragmatic two arm cluster RCT
Unit of randomisation		Family
Minimisation variables (if applicable)		Age group (all CYP aged 8-11 / all CYP aged 12-14 / CYP aged 8-11 and 12-14), Minority ethnic group status of one or both parents (yes / no), relationship status (separated/intact)
Primary outcome	variable	a) Child internalising and externalising
	measure (instrument, scale, source)	a) Parent reported SDQ, total difficulties scale (Goodman, 1997)
Secondary outcome(s)	variable(s)	
 b) Child psychological well-being c) Parent report IPC d) Child perception of IPC e) Parent anger f) Parent mentalising capacity g) Parenting style h) Parent emotional adaptation to separation (separated parents only)
	measure(s) (instrument, scale, source)	
 b) Stirling Children’s Well-being Scale (Liddle & Carter, 2015) c) O’Leary-Porter Scale (Porter & O’Leary, 1980) d) Perceptions of Interparental Conflict-Intensity/Frequency Scale (PIC-I/F) (Kline, Wood & Moore, 2003) e) Dimensions of Anger Reactions- Revised (DAR-R; (Nederlof, Hovens, Muris & Novaco, 2009) f) Parental Reflective Function Questionnaire (Luyten et al., 2009) g) Parenting Scale Short Form (PS-8) (Kliem et al., 2019), a short form of the Parenting Scale (Arnold et al., 1993) h) Emotional Adaptation to Relationship Dissolution Assessment (Millings et al., 2020)

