Baseline for primary outcome	variable	Scores at baseline (pre-randomisation) on variables listed above
	measure (instrument, scale, source)	As above
Baseline for secondary outcome	variable	Scores at baseline (pre-randomisation) on variables listed above
	measure (instrument, scale, source)	As above

Randomisation

Randomisation will be conducted on all consenting referrals (referral and consent procedure are outlined below) as they occur. Because recruitment will be rolling, classic random stratification is not feasible. We will therefore use minimisation (Scott et al., 2002; Altman & Bland, 2005) whereby allocation is random initially and then systematic to minimise differences between groups across a few specified strata within LAs, specifically, child age, parent minority ethnic group status, and relationship status (intact or separated). In the context of rolling recruitment, a minimisation approach will best ensure that the MBT-PP and TAU samples are comparable in terms of the specified strata. The minimisation will be undertaken using the MininPy software.

Participants

Participants will be referred to the project by LA staff (e.g., Early Help practitioners) through an online form. LA staff will be provided with information/training about the project detailing that it is for:

- Parents experiencing high intensity, frequent and unresolved IPC, who have at least one child aged between 8 and 14 years old
- They do not have to live together, or be in a current relationship, but should be willing to think about how they can improve their relationship with their co-parent.
- Parents will need to consent to the referral being made and have an understanding that the work will focus on the quality of the relationship with their co-parent.
- Parents must understand that:
 - This is a research project

- They will be randomly allocated to receive either support from Early Help which will involve using an online therapeutic resource or the MBT-PP intervention, which is delivered online.
- They will need to fill in questionnaires before the start, at the end, and then three months after they finish.
- They will receive vouchers to thank them for their time, once they have completed all the questionnaires.
- They will need to be willing and able to attend either 10 sessions of MBT-PP therapy or engage with the digital resources as directed by Early Help staff

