The smallest effect size that our proposed CRT design could detect with a specified statistical significance ($\alpha < 0.05$, two tailed) and statistical power ($1 - \beta = 80\%$ or higher) is known as the Minimum Detectable Effect Size (MDES) and can be calculated using Equation 1 adapted from Spybrook et al (2016). We estimated the MDES for our design using this equation and checked this using the PowerUp! software (Dong et al., 2015).

Equation 1:

$$MDES_{2LCRT} \sim M_{J-m-2} \sqrt{\frac{1}{P(1-P)}} \sqrt{\frac{ICC(1 - R_{Fam}^2)}{J} + \frac{(1 - ICC)(1 - R_{CYP}^2)}{nJ}}$$

For a CRT design, the MDES is influenced by:

- n = number of children per family (estimated as **2**); J = number of families (see below)
- P = proportion of families allocated to intervention group (**=0.50**)

- m = number of (level 2) covariates used (which will include: group membership, family-level pre-test and all variables used for minimisation, ~ 11 variables)
- M_{J-m-2} is the group effect multiplier value of the t-distribution for a 2-tailed test with $\alpha=0.05$ & $\beta=0.80$
- ICC is the family level ICC (proportion of variance of the outcome at level 2) ~ this is unknown but estimated at between 0.01 and 0.15 (to be updated with empirical estimates from internal pilot)
- R_{CYP}^2 = proportion of within-family child level variance that is reduced by covariate(s) - pupil level explanatory power and R_{Fam}^2 = proportion of between-family variance that is reduced by covariate(s) - family level explanatory power. These are also unknown and will be updated with empirical estimates from the internal pilot. For these a priori MDES estimates, we have assumed that $R_{CYP}^2 = R_{Fam}^2$ and allowed the values to vary between 0.25 and 0.49 (based on an assumed pre-post test correlation of between 0.50 and 0.70).

The number of families (J) has been allowed to vary between 200 and 350. This is the ITT sample of families without taking account of possible attrition (see below).

Table 3 shows a range of MDES estimates across 20 cells. MDES estimates of 0.22 SDs or lower are highlighted because, informed by meta-analyses of child outcomes for family therapy (van der Pol et al. (2017), parent mindfulness interventions (Burgdorf et al., 2019), and co-parenting interventions (Eira Nunes et al., 2020), we expect MBT-PP to produce a small effect on child outcomes.

Table 3. MDES estimates for a 2-level Clustered RCT with randomisation at the family level.

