This trial is running in 3 local authorities, Bristol, Dorset, and Bournemouth, Christchurch, and Poole (BCP). In each local authority, this evaluation funds a 'Gateway Lead' post. Postholders are staff with experience of working with CYP and families and have backgrounds in primary teaching and family support.

Gateway Leads have created referral pathways into the project and promoted awareness of the project in schools and other relevant local authority staff. When referred, families are screened for eligibility against exclusion and inclusion criteria and taken through the consent

process. Once consent is obtained, families complete baseline assessments, and are subsequently randomly allocated to receive either MBT-PP or TAU. Allocation is conducted by the evaluator according to a minimisation protocol to ensure a balanced sample. Families then undergo their allocated treatment. Once treatment has completed, families complete post-intervention assessments. Follow up assessments are completed 3 months later.

The primary outcome variable for this trial is the ‘Total Difficulties’ (TD) subscale of the Strengths and Difficulties Questionnaire (SDQ; Goodman, 1997) obtained from the mothers’ post-intervention assessment, reporting on the CYP. As such, analyses will focus on comparing mothers’ post-intervention TD scores between MBT-PP and TAU. Secondary outcome variables are fathers’ post-intervention TD score; and child psychological well-being (as measured by the Stirling Children’s Well-being Scale, Liddle & Carter, 2015).

The trial is also assessing proposed mechanisms of action, by assessing: parent report IPC (as measured by the O’Leary-Porter Scale, OPS, Porter & O’Leary, 1980, adapted as described in the protocol); child perception of IPC (as measured by the Perceptions of Interparental Conflict-Intensity/Frequency Scale, PIC-I/F, Kline, Wood & Moore, 2003); parent anger (as measured by the Dimensions of Anger Reactions-Revised, DAR-R, Nederlof et al., 2009); parent mentalising capacity (as measured by the Parental Reflective Function Questionnaire, PRFQ, Luyten et al., 2009); parenting style (as measured by the Parenting Scale Short Form, PS-8, Kliem et al., 2019); and, for separated parents only, parent emotional adaptation to separation (as measured by the Emotional Adaptation to Relationship Dissolution Assessment, EARDA, Millings et al., 2020).

Table 1. Trial design overview

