will not result in different estimates of coefficients (and hence impact) compared with using raw scores at CYP level and aggregated mean scores at the family/parent level but brings other statistical advantages. Hedges & Hedberg (2007) note that using cluster (mean) centring results in more stable estimates of variance components when covariate values vary substantially across clusters. Centring also ensures no issues of multicollinearity because the correlation between the cluster- and CYP-level centred variables will be zero². Finally, centring results in a more realistic coefficient estimate for the constant term because this relates to a mean score (rather than a score of zero) on the T1 mothers SDQ-TD score.

Primary outcome analysis

A multilevel linear regression model will be used to estimate the impact of the Tavistock MBT-PP intervention, on mothers-reported SDQ total difficulties (SDQ-TD) score for their children. Whilst mothers-reported SDQ -TD score represents the single primary outcome for the impact evaluation, fathers SDQ-TD score will also be analysed as a secondary outcome (see below).

For the analysis of the primary outcome, an estimate of impact will be obtained from a hierarchical (multilevel) linear model described in equation 2.0:

$$[2.0] \quad Y_{ij} = \beta_0 + \beta_1 T_j + \beta_2 (X_{ij} - \bar{X}_j) + \beta_3 (\bar{X}_j - \bar{X}) + \beta_{4..7} [MIN DUM]_j + \vartheta_j' + \varepsilon_{ij}'$$

Where:

- Y_{ij} is the mothers reported SDQ-TD for CYP i in family j at T2 (16 weeks following minimisation).
- T_j is the family-level group identifier which will take the value 1 (=MBT) or zero (=TAU)
- β_1 is the coefficient that estimates the difference between the MBT and TAU groups adjusted for baseline scores and minimisation variables; i.e. $\beta_1 = (MBT - TAU)_{adjusted}$. The β_1 coefficient will be used to estimate the AITT (see below).
- X_{ij} is the mothers reported SDQ-TD for CYP i in family j at T1/baseline centred around \bar{X}_j , the family-level mean (i.e. $(X_{ij} - \bar{X}_j)$)
- \bar{X} is the family-level grand mean mothers reported SDQ-TD score used to centre \bar{X}_j , the family-level mean (i.e. $\bar{X}_j - \bar{X}$)
- $[MIN DUM]_j$ is the collection of four family-level dummy variables used in the minimisation; ages of CYP in family (two variables); whether one parent was not White British (one variable) and relationship status (one variable).

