Table 4 above lists a total of 35 secondary outcomes. For all 35 secondary outcomes, an ITT approach will be taken.

For the analysis of all secondary outcomes, an estimate of impact will be obtained from a hierarchical linear model described in equation 3.0:

$$[3.0] \quad Y_{ij} = \beta_0 + \beta_1 T_j + \beta_2 (X_{ij} - \bar{X}_j) + \beta_3 (\bar{X}_j - \bar{X}) + \beta_{4..7} [MIN DUM]_j + \vartheta_j + \varepsilon_{ij}$$

Where:

- Y_{ij} is secondary outcome score for CYP i in family j at T2 (16 weeks following minimisation).
- T_j is the family-level group identifier which will take the value 1 (=MBT) or zero (=TAU)
- β_1 is the coefficient that estimates the difference between the MBT and TAU groups adjusted for baseline scores and mimimisation variables; i.e. $(MBT - TAU)_{adjusted}$
- X_{ij} is the baseline score for the secondary outcome for CYP i in family j at T1/baseline centred around \bar{X}_j , the family-level mean (i.e. $(X_{ij} - \bar{X}_j)$)
- \bar{X} is the family-level grand mean for the secondary outcome and used to centre \bar{X}_j , the family-level mean (i.e. $\bar{X}_j - \bar{X}$)
- $[MIN DUM]_j$ is the collection of four family-level dummy variables used in the minimisation; ages of CYP in family (two variables); whether one parent was not White British (one variable) and relationship status (one variable).
- $\beta_{4..7}$ are the coefficient estimates for the four family-level dummy variables.
- ϑ_j and ε'_{ij} are random effects that remain at the school and pupil levels and are assumed to be distributed normally in the population with zero means, variances σ_c^2 and τ_c^2 respectively.

Table 6 summarises the ITT analysis for the fathers SDQ-TD secondary outcome as an example, a similar approach will be used for all secondary outcomes at T2.

Table 6. Example analysis model for fathers SDQ-TD primary outcome (RQ1b)

Analysis and Sample	Level 1 (CYP) Covariates	Level 2 (Family) Covariates	Outcome Variable

Empty model			CYP level fathers SDQ-TD (raw) score at T2 (16 weeks following minimisation)
Final Model	Fathers SDQ-TD score at T1/baseline (Centred around family mean)	Mean fathers SDQ-TD score at T1/baseline (Centred around grand mean) Group membership (MBT or TAU) Four Minimisation Variables: CYP ages (2), parental ethnicity (1), relationship status (1).	CYP level fathers SDQ-TD (raw) score at T2 (16 weeks following minimisation)

Subgroup analyses

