Compliance will be measured at the family level and is defined as families where at least one parent received 6+ sessions of MBT-PP (i.e., a family where two parents received up to 5 sessions each would not be classed as compliant). Six sessions is selected as the cut off due to previous research finding significant effects when 6 sessions was used as the minimum clinical offer (Hertzmann et al., 2016)

Compliance is assumed to be one-sided. Specifically, whilst it is possible for a family allocated to the MBT group to have not met the pre-specified compliance criteria (i.e., attending 6+ MBT-PP sessions), it is not possible for families allocated to the TAU group to have experienced any of the MBT-PP programme.

Compliance will be operationalised as a family-level binary variable which identifies CYPs in families classed as ‘compliant’ (= 1) and ‘not compliant’ (= 0). This will be used for the Compliers Average Causal Effect (CACE) analysis. An instrumental variable (IV) approach will be used with two-staged least squares to obtain CACE estimates. The first stage models the compliance binary outcome with the treatment indicator (T_j) included as a covariate. The predicted value for the compliance outcome (C'_j) is then entered into a second stage model in place of the treatment indicator (T_j) as described in equations 6.1 (step 1) and 6.2 (step 2) below.

$$[6.1] \quad C_j = \beta_0 + \beta_1 T_j + \beta_2 (X_{ij} - \bar{X}_j) + \beta_3 (\bar{X}_j - \bar{X}) + \beta_{4..7} [MIN DUM]_j + \vartheta'_j + \varepsilon'_{ij}$$

$$[6.2] \quad Y_{ij} = \beta_0 + \beta_1 C'_j + \beta_2 (X_{ij} - \bar{X}_j) + \beta_3 (\bar{X}_j - \bar{X}) + \beta_{4..7} [MIN DUM]_j + \vartheta'_j + \varepsilon'_{ij}$$

These two stages are included in the STATA ‘ivregress’ command. Standard errors of estimates will be adjusted for clustering of CYP in families using the ‘vce (cluster robust)’ subcommand.

Intra-cluster correlations (ICCs)

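### The protocol describes minimisation within local authorities, but no SAP model contains a local authority term: confirm the set-up and add two dummies (a free improvement, minor in size)

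*SAP*

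**What the plan says.** **Allocation.** Protocol, Randomisation: "allocation is random initially and then systematic to minimise differences between groups across a few specified strata within LAs". The sentence goes on to name child age, parent minority ethnic status and relationship status. SAP, Design overview: "This trial is running in 3 local authorities".

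**Design tables.** Protocol Table 2 gives the minimisation variables as age group, then "Minority ethnic group status of one or both parents (yes / no), relationship status (separated/intact"). SAP Table 1 repeats these three as stratification variables. Neither table names LA.

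**Models.** In SAP equation 2.0 the minimisation term "is the collection of four family-level dummy variables used in the minimisation; ages of CYP in family (two variables"), with one further dummy each for parental ethnicity and relationship status. Equation 3.0 (secondary outcomes) carries the same set: its last group of terms "are the coefficient estimates for the four family-level dummy variables". Equations 4.0 (subgroups), 5.0 (time between assessments), 6.1 and 6.2 (CACE) reuse that set, and Tables 5 to 8 list the same covariates. LA is in none of them. It is also absent from the variables named under Imbalance at baseline, and that list supplies the drop-out model under Missing data.

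**Stated intention.** The SAP describes the treatment coefficient in equation 2.0 as adjusted for baseline scores and the minimisation variables. The protocol's sample size section counts among its level-2 covariates group membership, "family-level pre-test and all variables used for minimisation, ~ 11 variables". The SAP count is 6. The SAP gives no reason for leaving LA out.

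**The concern.** Balancing three factors separately within each LA also brings the arms close to balance on LA itself. On the protocol's wording, LA is therefore part of the allocation scheme, and the SAP's own principle of adjusting for minimisation variables would bring it into the model.

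When a prognostic factor is balanced by design and then omitted, the treatment estimate benefits from the balance but the model-based standard error does not. The LA variance stays in the residual, the standard error is too large, and the test rejects less often than its nominal 5%.

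LA could plausibly be prognostic. Each LA has its own Gateway Lead and referral pathway, LA staff deliver treatment as usual, and only two of the three LAs already used the digital resources on which it is based. What is at stake is a small amount of precision, in a trial whose target has been cut from 350 to 250 families.

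**Working it through.** **Inputs** (SAP, Sample size calculations): J = 250 families, n = 1.4 children per family, P = 0.50, ICC = 0.27, R² = 0.61 (family) and 0.75 (child), m = 6, two-sided alpha 0.05, power 0.80. The share of variance due to LA is not in the documents. It is an assumption here, s = 0, 2, 5 or 10% of the between-family variance left after baseline adjustment.

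**1. Reproduce the plan's figure (SAP equation 1.0).**
- Family component: 0.27 × (1 − 0.61) = 0.1053.
- Child component: 0.73 × (1 − 0.75) / 1.4 = 0.1304.
- Sum: 0.2357. SE = 2 × √(0.2357 / 250) = 0.0614.
- Multiplier with 250 − 6 − 2 = 242 df: 2.813. MDES = 2.813 × 0.0614 = 0.173, stated as 0.17.

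The other SAP Table 3 figures also reproduce (0.290, 0.224, 0.193, 0.158, 0.146 and 0.136 for 90, 150, 200, 300, 350 and 400 families).

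**2. Cost of two LA dummies.** With m = 8, df = 240 and the multiplier is still 2.813. The MDES is 0.1727 either way.

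**3. Effect on the standard error.** LA can remove variance only from the family component, which is 0.1053 / 0.2357 = 45% of the squared standard error. The overstatement ratio is therefore r = √[0.2357 / (0.1053(1 − s) + 0.1304)].

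**4. Effect on the test.** This treats the arms as balanced on LA.
- Type I error with LA omitted: 2 × [1 − Φ(1.96r)].
- Power at the stated MDES with LA included: Φ(2.80r − 1.96).
- Power with LA omitted: Φ[(2.80 − 1.96)r] = Φ(0.84r), because the estimate is already less variable than the model believes.

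| Assumed LA share s | r | SE overstated by | Type I, LA omitted | Power, LA omitted | Power, LA included | MDES, LA included |
|---|---|---|---|---|---|---|
| 0% | 1.000 | 0% | 5.0% | 80% | 80% | 0.173 |
| 2% | 1.004 | 0.4% | 4.9% | 80.1% | 80.3% | 0.172 |
| 5% | 1.011 | 1.1% | 4.7% | 80.2% | 80.8% | 0.171 |
| 10% | 1.023 | 2.3% | 4.5% | 80.5% | 81.7% | 0.169 |

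**5. Check by simulation.** 4,000 runs per setting, 250 families, deterministic minimisation within three LAs, regression on family means. Here the LA share is of the whole residual variance of family means, a larger quantity than s above, so the effects are larger at the same percentage. With LA omitted, type I error was 0.049, 0.049, 0.038 and 0.029 at shares of 0, 5, 10 and 20%. With LA included it stayed near 0.05. Power at 0.17 SD was 0.79, 0.79, 0.80 and 0.82 omitted, against 0.79, 0.80, 0.83 and 0.88 included. The direction agrees with the table.

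**The case against.** **LA may not have been an allocation factor.** The case rests on one phrase in one protocol sentence. Both design tables, the SAP's count of four minimisation dummies and its baseline-balance section all omit LA. The protocol's count of about 11 covariates does not settle it: group, pre-test, four dummies and two for LA make 8. This stands. The documents conflict and do not show how the software was set up, so confirmation comes first.

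**LA may not matter after adjustment.** Parental ethnicity is already in the model, so the different ethnic mix of the LAs adds little. Baseline SDQ enters at both levels with high pilot R², which should absorb much of any difference in severity. Earlier use of the digital resources in two LAs bears on the comparator and could make the treatment effect differ by LA, which main-effect dummies would not capture. The protocol also plans training in all three LAs. This stands too: zero belongs in the range, and a loss of precision is possible rather than shown.

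**A stronger reading.** A reader might infer that the mismatch threatens the validity of the primary result, or that LA variance translates one-for-one into the squared standard error. Neither holds. Omitting a balanced factor leaves the ITT estimate unbiased and does not inflate false positives. Only 45% of the squared standard error lies between families, so a 10% share overstates the standard error by 2.3%. The formula 1/√(1 − 0.10) would give 5.4%.

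**Conclusion.** The inconsistency is real: the protocol describes allocation within LAs, while the design tables and every specified model leave LA out. The consequence is conditional and small. It requires that LA was used in allocation and that LA predicts mother-reported SDQ after baseline adjustment. The documents establish neither. Over the assumed range of 0 to 10% of conditional between-family variance, the standard error is overstated by at most 2.3%, type I error falls no lower than about 4.5%, and including LA raises power from 80.5% to 81.7% at the top of the range. This is a free improvement, minor in size. It is best specified before the data are analysed, since adding LA afterwards would be a post hoc choice of covariate.

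**What to change.** 1. Confirm from the minimisation software's configuration whether LA was used, and reconcile the protocol's Randomisation section with protocol Table 2 and SAP Table 1. If it was not used, correct the Randomisation section.
2. Add two LA dummies to equations 2.0, 3.0, 4.0, 5.0, 6.1 and 6.2 and to Tables 5 to 8.
3. Add LA to the baseline-balance list and to the drop-out model.
4. Change m from 6 to 8 in the SAP's power section.

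The cost is SAP wording and two degrees of freedom. The MDES at 250 families remains 0.173, so the stated 0.17 and the recommended sample size do not change.
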